### 5.2.5 Pain Catastrophizing Scale (PCS) at 4 weeks and 8 weeks after SOT

PCS is a widely-used, validated 13-question instrument to assess rumination (4 questions), magnification (3 questions), and helplessness (6 questions). The survey asks participants to think back on painful experiences in the past and reflect on how often they had specific thoughts or feelings. Each question is scored on a 0-4 scale with 0 = "not at all" and 4 = "all the time". Higher scores indicate a greater tendency towards catastrophizing pain, which has been correlated with worse pain and response to pain therapies.

The analysis of treatment effect on PCS examines the difference in the mean percent improvement from baseline at specified intervals in Group #1 relative to that of Group #2. The baseline PCS score will be compared to the PCS score at the specified intervals after start of therapy. The mean percent improvement in Group #1 at 4 weeks and 8 weeks will be compared to

Group #2 at 4 weeks and 8 weeks, respectively. The difference between groups will be evaluated with a Wilcoxon rank-sum test. The null hypothesis is that there is no difference in mean percent improvement between the two treatment groups, versus the alternative hypothesis, that the mean percent improvements differ from one another. Testing will be conducted at the 0.05 level of significance.

# 5.2.6 Patient Global Impression of Change at 4 weeks, 8 weeks, and 3, 6, 9, and 12 months after SOT

The analysis of treatment effect on the PGIC compares the rank scores (of 7 possible ranks, ranging from -3 to 0 to +3, where -3 is very much worse, 0 is no change, and +3 is very much improved) of Group #1 to Group #2. The mean rank score of Group #1 at 4 weeks, 8 weeks, and 3 months will be compared to Group #2 at 4 weeks, 8 weeks, and 3 months, respectively. The mean rank score of Group #1 at 3, 6, and 12 months will be compared to Group #2 at 3 months (the longest follow-up before crossover). The difference between groups will be evaluated with a Wilcoxon rank-sum test. The null hypothesis is that there is no difference in the mean rank score between the two treatment groups, versus the alternative hypothesis, that the mean rank scores differ from one another. Testing will be conducted at the 0.05 level of significance.

### 5.2.7 Pain Interference at 8 weeks, and 3, 6, 9, and 12 months after SOT

The analysis of the treatment effect on pain interference compares the proportion of subjects who successfully achieve  $\geq 50\%$  reduction in average pain interference score in Group #1 at each time point relative to that in Group #2 based on a Fisher's exact test. Relief of pain interference will be evaluated using the average pain interference (BPI-SF Question #9). The baseline average pain interference score will be compared to the average pain interference score at each specified interval after start of therapy to determine the percent reduction in pain interference. To be considered a success, subjects must have  $\geq 50\%$  reduction in the average pain interference score. The proportion of success in Group #1 at 4 weeks, 8 weeks, and 3 months will be compared to Group #2 at 4 weeks, 8 weeks, and 3 months, respectively. The proportion of success in Group #1 at 3, 6, and 12 months will be compared to Group #2 at 3 months (the longest follow-up before crossover). The null hypothesis is that there is no difference in proportions of success between the two treatment groups, versus the alternative hypothesis, that the proportions of success differ from one another. Testing will be conducted at the 0.05 level of significance.

# 5.2.8 Western Ontario and McMaster Universities Osteoarthritis Index (WOMAC) at 8 weeks, 3, 6, 9, and 12 months after SOT

[figure not shown]
The analysis of treatment effect on function (*i.e.*, physical recovery) compares the proportion of subjects who successfully achieve  $\geq$  33% improvement[3-5] in average WOMAC score in Group #1 at each time point relative to that in Group #2 based on a Fisher's exact test. The WOMAC questionnaire assesses physical recovery and includes 24 items assessing pain, stiffness, and difficulty with daily activities. Each item is scored on an 11-point numerical rating scale from 0-10 with lower numbers indicating improved physical recovery, and the total score is calculated.

[figure not shown]
The WOMAC scores will be collected at baseline and compared to the WOMAC scores at each specified interval after start of therapy to determine the percent improvement (*i.e.*, reduction in score) in physical recovery. To be considered a success, subjects must have  $\geq 33\%$  reduction in the WOMAC score. The proportion of success in Group #1 at 8 weeks and 3 months will be compared to Group #2 at 8 weeks and 3 months, respectively. The null hypothesis is that there is no difference in proportions of success between the two treatment groups, versus the alternative hypothesis, that the proportions of success differ from one another. Testing will be conducted at the 0.05 level of significance.

# 5.2.9 Six Minute Walk Test (6MWT) at 8 weeks and 3 months after SOT

The 6MWT measures the distance walked in 6 minutes and will be used to assess walking speed and endurance. Subjects that are unable to complete the 6MWT will be assigned a score of 0 for that visit. The analysis of treatment effect on the 6MWT examines the difference in the mean percent improvement from baseline at specified intervals in Group #1 relative to that of Group #2. The baseline 6MWT score will be compared to the 6MWT score at the specified intervals after start of therapy. The mean percent improvement in Group #1 at 8 weeks and 3 months will be compared to Group #2 at 8 weeks and 3 months, respectively. The difference between groups will be evaluated with a Wilcoxon rank-sum test. The null hypothesis is that there is no difference in mean percent improvement between the two treatment groups, versus the alternative hypothesis, that the mean percent improvements differ from one another. Testing will be conducted at the 0.05 level of significance.

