3.2 Sample Size Rationale

### 4.0 Study Hypotheses

The primary hypothesis is tested under a significance level of 0.05 (two-sided). All secondary hypotheses are considered exploratory in nature and claims of statistical significance will not be made based on the statistical tests. Any hypotheses tested will be at a significance level of 0.05 (two-sided) with no adjustments for multiple comparisons. Primary, secondary, and exploratory endpoints are described in Section 5.0 (Endpoint Analyses) and Section 8.0 (Efficacy Analyses), including the data collection instruments, data analysis techniques (e.g., thresholds for success in a given outcome), and statistical tests for each endpoint.

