where u G1 and u G2 are the mean scores for PGIC at specified intervals after start of therapy (4 weeks, 8 weeks, and 3, 6, and 12 months after SOT in Group #1 and 4 weeks, 8 weeks, and 3 months after SOT in Group #2).

7) Pain Interference (BPI-9) at specified intervals after start of therapy

H0: 
$$p_{G1} - p_{G2} = 0$$
 vs.

Ha: 
$$p_{G1} - p_{G2} \neq 0$$

where p G1 and p G2 are the proportions of success for pain interference at specified intervals after start of therapy (4 weeks, 8 weeks, and 3, 6, 9, and 12 months after SOT in Group #1 and 4 weeks, 8 weeks, and 3 months after SOT in Group #2).

8) Physical recovery (Western Ontario and McMaster Universities Osteoarthritis Index; WOMAC) at specified intervals after start of therapy

$$H_0$$
:  $p_{G1} - p_{G2} = 0$  vs.

$$H_a$$
:  $p_{G1} - p_{G2} \neq 0$ 

where p G1 and p G2 are the proportions of success for WOMAC at specified intervals after start of therapy (8 weeks, and 3, 6, and 12 months after SOT in Group #1 and 8 weeks and 3 months after SOT in Group #2).

9) 6MWT at specified intervals after start of therapy

H0: 
$$u_{G1} - u_{G2} = 0$$
 vs.

Ha: 
$$u_{G1} - u_{G2} \neq 0$$

where u G1 and u G2 are the mean percent improvement on the 6MWT at specified intervals after start of therapy (8 weeks and 3 months after SOT).

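### SAP 5.2.9 scores a 6MWT non-completer as 0 with no visible exemption for baseline, then tests percent improvement from baseline; the visible text has no convention for a zero baseline

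*SAP*

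**What the plan says.** SAP 5.2.9 sets the scoring rule: "Subjects that are unable to complete the 6MWT will be assigned a score of 0 for that visit". It then defines the outcome: "The analysis of treatment effect on the 6MWT examines the difference in the mean percent improvement from baseline at specified intervals". The inputs are fixed by "The baseline 6MWT score will be compared to the 6MWT score at the specified intervals after start of therapy", and the test by "The difference between groups will be evaluated with a Wilcoxon rank-sum test". Hypothesis 9 in SAP 4.2 is framed on the same variable at 8 weeks and 3 months. Protocol 4.4 lists the 6MWT among the outcome measures and names baseline as a collection time.

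On status, SAP 4.0 says "All secondary hypotheses are considered exploratory in nature and claims of statistical significance will not be made based on the statistical tests". The same section says that Sections 5.0 and 8.0 describe the endpoints, "including the data collection instruments, data analysis techniques (e.g., thresholds for success in a given outcome), and statistical tests for each endpoint". In the public copy most of Section 8 is withheld; 8.2 on missing data survives only as a heading.

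SAP 5.2.5 uses the same kind of outcome for the PCS: "The analysis of treatment effect on PCS examines the difference in the mean percent improvement from baseline at specified intervals".

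**The concern.** The scoring rule can itself create the zero that the outcome then divides by. A subject who cannot complete the walk at baseline scores 0, and percent improvement from 0 does not exist. Someone must then choose what to do: drop the subject, enter some fixed value, or let an infinite value rank as the best outcome in the trial. A single such value also leaves that arm's mean percent improvement undefined. If the choice is made after unblinding, it is made with the results in view.

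The PCS has the same gap. Its 13 items each start at 0, so a baseline total of 0 is possible.

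**Working it through.** The documents give no sample size, SD or non-completion rate for the 6MWT, so there is no planned figure to reproduce. The rule is applied directly, and all sizes below rest on assumed inputs.

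**1. The outcome under the rule.** Percent improvement = 100 × (follow-up − baseline) / baseline. Example distances are assumed.

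| Baseline | Follow-up | Percent improvement | Change in metres |
|---|---|---|---|
| 300 m | 360 m | 100 × 60/300 = +20% | +60 |
| 300 m | 0 (not completed) | 100 × (−300)/300 = −100% | −300 |
| 0 (not completed) | 300 m | 300/0, infinite | +300 |
| 0 (not completed) | 50 m | 50/0, infinite | +50 |
| 0 (not completed) | 0 (not completed) | 0/0, indeterminate | 0 |

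Only the zero-baseline rows fail. Subjects who recover to 50 m and to 300 m cannot be ordered against each other. Change in metres is defined in every row.

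**2. How many subjects.** If 1 to 8% of 50 to 80 subjects cannot complete at baseline (assumed), the expected number of undefined outcomes runs from 50 × 0.01 = 0.5 to 80 × 0.08 = 6.4. The chance of at least one is 1 − 0.99^50 = 39% at the low end and 1 − 0.92^80 = 99.9% at the high end.

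**3. Does the choice of convention matter?** Simulation inputs, all assumed: baseline distance mean 350 m and follow-up mean 370 m, SD 100 m, floor 50 m; correlation 0.5 or 0.7; 25 or 40 per arm; effect +45 m; two-sided 0.05; 2,000 replicates. Zero baselines are placed at random across the arms. Share of trials in which excluding these subjects and ranking them best fall on opposite sides of 0.05:

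| Zero baselines | Verdict differs |
|---|---|
| 1 | 7.4–8.9% |
| 2 | 8.7–12.3% |
| 3 | 11.2–14.0% |

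These shares are conditional on zeros occurring. At the low end of step 2, the unconditional figure is about 0.39 × 7.4–8.9%, or roughly 3%. With more zeros it grows: a separate simulation (50 per arm, 8% baseline non-completion, 30 m effect) expects 100 × 0.08 = 8 zeros, and the two conventions differed in about 19% of runs. Rejection rates there were 61% when dropped and 51% when ranked best.

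**4. The alternative analysis.** The inputs are those of step 3, with an effect of +45 m or ×1.12 and non-completion of 0, 4 or 8% at each visit. The planned test excludes zero baselines. ANCOVA uses metres, with the distance reached counted for early stoppers.

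| Per arm | ANCOVA of metres | Planned percent-change test |
|---|---|---|
| 25 | 33–60% power | 22–43% power |
| 40 | 51–80% power | 36–64% power |

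The gain is 12 to 20 points at 0% non-completion, 10 to 19 at 4% and 10 to 18 at 8%. Rank ANCOVA gains 8 to 19 points. Null rejection rates are 4.3–5.5% (planned), 4.6–5.6% (ANCOVA) and 4.6–5.7% (rank ANCOVA).

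The gain is already present at 0% non-completion, so it comes from adjusting for baseline and not from repairing the zero. Recording distance but keeping the percent-change test moves power by only −2.6 to +0.9 points.

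One limit applies. When the design was rerun with the assigned zeros left in at both visits, linear ANCOVA lost most or all of its advantage at 4 to 8% non-completion and in some settings fell below the planned test. Rank ANCOVA kept an advantage in every setting.

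**The case against.** The strongest reply is that this may never arise and may already be covered. The SAP does not name baseline in the scoring rule, and the heading of 5.2.9 lists only 8 weeks and 3 months. Section 8 is largely withheld, as are parts of the exclusion criteria, the Visit 1 procedures and the schedule in Appendix A. Any of these could hold a convention or a walking requirement. The visible inclusion criterion on being able to meet the study's demands may screen out some subjects who cannot walk. No significance claim is planned, so crossing 0.05 changes no formal conclusion.

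Much of this stands. A reader might infer that the SAP expressly zeroes the baseline, or that a convention is missing from the full plan; the public documents show neither. What remains is that the rule exempts no visit while the outcome requires a baseline score. Also, an assigned 0 is a score and not a missing value, so a missing-data rule would not obviously cover it.

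Three further inferences do not hold:

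- **The −100% at follow-up is an error.** It is a defined value and, in the rank-sum test, simply the worst tied rank, which may be intended. Whether it also covers someone who walks part of the way depends on what being unable to complete means, and the visible text does not say.
- **Disagreement is 15 to 28%.** That figure comes from also counting 0% change and worst rank as candidate conventions. Worst rank is implausible for a subject who may have walked at follow-up.
- **Pain interference (5.2.7) shares the problem in practice.** Subjects enter with persistent knee pain above a threshold, so a mean interference of exactly 0 is unlikely.

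It is also fair to say that a percent-change rank test is legitimate and that one sentence would close the gap. The ANCOVA proposal rests mainly on its separate gain in precision.

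**Conclusion.** The concern holds in limited form and is minor. On the plain reading of 5.2.9, a zero baseline gives an undefined outcome, and the visible text does not resolve it. The 7 to 14% disagreement between excluding and ranking best is conditional on one to three zero baselines and on the assumed distances, correlation, effect and arm sizes. The true frequency is unknown and could be nil. The planned test holds its type I error in the simulations, and the primary endpoint is unaffected.

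**What to change.** In SAP 5.2.9 and hypothesis 9, compare 6MWT distance in metres at 8 weeks and at 3 months by ANCOVA with treatment and baseline distance. Report the adjusted difference with its 95% CI, with rank ANCOVA as the check. A baseline of 0 then stays in the analysis without a special rule. Keep percent improvement as a descriptive summary, with the number of undefined values per arm.

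Recording the distance reached at an early stop is optional and depends on how being unable to complete is defined. If it is not recorded and zeros are more than occasional, give the rank ANCOVA more weight than the linear model.

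If percent improvement stays the tested scale, state the zero-baseline convention in 5.2.9 before unblinding, or cite it if withheld text holds one. Add the same sentence to 5.2.5 for the PCS and leave its planned test as it is.

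The cost is SAP wording and programming, plus a form field only if early-stop distance is wanted and not already captured. The downside is that the tested scale is no longer percent improvement, and a distance at an early stop is not a full six-minute distance.

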### **5.2.10** Exploratory Analyses

### 6.2 Full Analysis Set

The Full Analysis Set (using a modified Intent to Treat approach) will include all subjects who sign a consent form, are randomized, and continue to meet eligibility criteria prior to the time of the lead placement procedure. All patients implanted with at least 1 lead with available data in weeks 5-8 will be analyzed according to the treatment group to which they were randomized.

Subjects who had a partial knee replacement or a revision knee replacement are excluded

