### 4.3 Sample Size and Justification

Up to 15 sites will participate in this study. Up to individuals will be enrolled as subjects and randomized to either Group #1 or Group #2. Subjects will be randomized at the start of Visit 2, after final eligibility is verified and before lead placement procedures begin.

Subjects who sign an informed

consent form and do not meet all study eligibility criteria will be considered screen failures and not count against the number of enrolled subjects.

4.4 Study Endpoints	4.4	Study	Endp	oints
---------------------	-----	-------	------	-------

Outcome measures will be collected from each subject in Group #1 (8 weeks of active stimulation) and Group #2 (8 weeks of sham stimulation) at Baseline and at specified follow-up visits

To support the study endpoints, the following outcome measures will be used:

- 1. Brief Pain Inventory, Short Form (BPI-SF)
- 2. Diary
  - Average affected Knee Pain (rated using BPI Question 5)
  - Medication affecting pain, including reason for use
- 3. Western Ontario McMaster Universities Osteoarthritis Index (WOMAC)
- 4. Patient Global Impression of Change (PGIC)
- 5. Pain Catastrophizing Scale (PCS)
- 6. 6 Minute Walk Test (6MWT)

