### 4.4.1 Primary Endpoints

### 4.4.1.1 Primary Efficacy Endpoint

The primary efficacy endpoint will be average post-operative pain, for primary TKR subjects only, in the affected knee from weeks 5-8 of the treatment period (in both Group #1 and Group #2) compared to baseline.

All subjects will record average knee pain scores (BPI-SF Question #5) for the affected knee in diaries Subjects will record one pain score per day. For each subject, the 7-day baseline diary collection period will be used to calculate the mean of the "average pain." Each randomized subject must obtain ≥ 50% reduction during weeks 5-8 of the treatment period relative to the baseline score to be considered a success.

The primary endpoint of the study compares the proportion of successes of Group #1 (Treatment) relative to that of Group #2 (Control),

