### 5.0 Endpoint Analyses

Analyses of the primary and secondary effectiveness endpoints will be conducted on the full analysis set and the per-protocol population set at each specified study interval. The full analysis

set is considered the primary population for formal statistical hypothesis testing.
5.1 Primary Endpoint  Relief of postoperative pain will be evaluated using the average pain intensity. All subject will record pain scores daily for the qualifying knee (i.e., with total knee implant and qualifyin pain) in the 7-day diaries using BPI-SF Question #5. Data will be collected  Each subject must have ≥50% reduction is
pain relative to baseline to be considered a success in the primary efficacy endpoint analysis. Missing data will be handled according to Section 8.2. The primare endpoint analysis will be based upon the Full Analysis Set, including imputation for missing data due to missed visits and early termination. An analysis will also be performed based on the Perotocol population,
Group #1 will receive active stimulation and Group #2 wi receive sham stimulation during the 8-week home trial.
The primary endpoint compares the proportion of subjects in Group #1 relative to that in Group #2 that achieve $\geq 50\%$ reduction in pain from baseline to Weeks 5-8 of the home trial using Fisher's exact test. The null hypothesis (H 0 ) is that the PNS treatment (Group #1, activational stimulation) is equal to the control (Group #2, sham stimulation) in providing pain relief. The alternative hypothesis (H a ) is that Group #1 has a proportion of successes that is not equal to the

 $H_0$ : proportion of successes in Group #1 = proportion of successes in Group #2  $H_a$ : proportion of successes in Group #2  $\neq$  proportion of successes in Group #2

If the proportion of successes in the PNS treatment is larger than the proportion of successes in the control during the Weeks 5-8 of the home trial and statistically significantly different (p < 0.05, two-sided), then the null hypothesis is rejected at the 0.05 level of significance, which will indicate that the therapeutic effect is clinically significant and superior to the placebo effect[2].

proportion of successes in Group #2.

treatment effect for time from TKR.

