### 6.3 Per Protocol Set

The per-protocol set of subjects defines a subset of the subjects in the Full Analysis Set who also meet the following criteria:

- Received correct treatment for group to which they were randomized
  Were implanted with two MicroLeads
  Reported coverage of in the region of postoperative
- pain during the primary endpoint period (Weeks 5-8) (Group #1 only)

  Not missing more than of average pain intensity (BPI-5) scores in the diaries during
- the primary endpoint period (i.e., Weeks 5-8 of home trial)

  Continued study eligibility throughout treatment period (Weeks 1-8)

Page 12 of 19

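### SAP 6.2 can be read as giving two denominators for the only confirmatory test: all randomized subjects still eligible before lead placement, or only those with a lead and weeks 5-8 data

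*SAP*

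**What the plan says.** - **SAP 5.0** makes the Full Analysis Set (FAS) the basis of the confirmatory test: the "set is considered the primary population for formal statistical hypothesis testing". SAP 4.0 treats all secondary hypotheses as exploratory, so the Fisher's exact test on weeks 5-8 success is the only confirmatory one.
- **SAP 6.2, first sentence**, admits all who consent, "are randomized, and continue to meet eligibility criteria prior to the time of the lead placement procedure". It sets no lead or data condition.
- **SAP 6.2, second sentence**: "All patients implanted with at least 1 lead with available data in weeks 5-8 will be analyzed according to the treatment group". The sentence ends by saying that this is the group assigned at randomization. It does not say what happens to other FAS members.
- **SAP 5.1**: the primary "endpoint analysis will be based upon the Full Analysis Set, including imputation for missing data due to missed visits and early termination". It adds: "Missing data will be handled according to Section 8.2". The body of 8.2 is not visible.
- **Protocol 4.3**: "Subjects will be randomized at the start of Visit 2, after final eligibility is verified and before lead placement procedures begin". A randomized subject can therefore have no lead.
- **SAP 6.4** builds the safety set by modifying the FAS. It adds subjects with attempted placement but no lead, and removes those with no attempt.

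**The concern.** A rule saying only that subjects are analyzed as randomized would not need to mention a lead or weeks 5-8 data. Because both are mentioned, the second sentence of 6.2 can be followed as a filter. A subject who leaves before week 5 would then be in the FAS by the first sentence and covered by 5.1's imputation for early termination, yet absent from the test.

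That would be an exclusion after randomization from the one test that decides the trial. If such losses differ between arms and are related to outcome, the comparison is biased. Leaving the wording open also allows the denominator to be chosen after the data are seen.

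**Working it through.** **1. The two readings side by side**

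| Randomized primary-TKR subject, eligible before placement | 6.2 first sentence with 5.1 | 6.2 second sentence as a condition |
|---|---|---|
| Lead placed, full weeks 5-8 diaries | analyzed | analyzed |
| Lead placed, some weeks 5-8 scores | analyzed | analyzed (no conflict) |
| Lead placed, stops before week 5 | analyzed, imputed | dropped |
| No lead placed | in the FAS | dropped |

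The readings part only in the last two rows. SAP 6.4 does not settle which is meant. Adding attempted-but-no-lead subjects to the FAS suggests that the FAS omits them, while removing never-attempted subjects suggests that it keeps them.

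**2. One-trial illustration**

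The visible text has no sample size, success rate, dropout figure or imputation rule, so there is no plan figure to reproduce and every input here is assumed: 50 per arm; 20 active v 12 sham successes; 10 v 2 subjects with no weeks 5-8 data. From the SAP come the two-sided Fisher's exact test and the 0.05 level.

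- Restricted: denominators 50 - 10 = 40 and 50 - 2 = 48; 20/40 v 12/48, p = 0.025.
- Imputed at each arm's own observed rate: active 20/40 = 50%, adding 10 × 0.50 = 5, so 25/50; sham 12/48 = 25%, adding 2 × 0.25 = 0.5, so 12/50 or 13/50; p = 0.012 or 0.023.
- Imputed at the sham rate in both arms: active adds 10 × 0.25 = 2.5, so 22/50 or 23/50; sham 12/50 or 13/50; p = 0.035 (23 v 12), 0.057 (22 v 12), 0.060 (23 v 13), 0.093 (22 v 13).
- Counted as non-successes: 20/50 v 12/50, p = 0.133.

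**3. Long-run illustration with no true difference**

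Assumed: true success 30% in both arms. Analyzed n per arm = round(n(1 - d)), where d is the proportion lost. If those lost are all non-successes, the analyzed success rate is 0.30/(1 - d), which is 0.375 at 20% loss and 0.316 at 5%. If loss is unrelated to outcome, it stays at 0.30. Binomial outcomes were enumerated exactly, counting Fisher rejections in favour of active. Loss is given as active v sham.

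| n per arm | All subjects, true outcomes | Restricted, 20% v 5% | Restricted, 5% v 20% | Restricted, 20% v 20% | Restricted, 20% v 5%, unrelated to outcome |
|---|---|---|---|---|---|
| 30 | 1.31% | 5.75% | 0.54% | 1.33% | 2.06% |
| 35 | 1.39% | 5.32% | 0.49% | 1.35% | 1.97% |
| 40 | 1.41% | 5.73% | 0.47% | 1.46% | 1.83% |
| 50 | 1.53% | 6.63% | 0.44% | 1.45% | 1.87% |
| 60 | 1.54% | 7.77% | 0.37% | 1.43% | 1.97% |

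Under the same outcome-related 20% v 5% loss, own-arm imputation gives about 6% at 30 per arm and 8% at 60, close to restriction. Sham-rate imputation gives about 2% to 3%. Both shift by up to a quarter of a percentage point with the rounding of imputed counts.

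**The case against.** The strongest reply is that the second sentence of 6.2 is a grouping rule. Its predicate is analysis by randomized group, and it does not say that other subjects are left out. This stands as a possible intent. A reader might infer that the SAP definitely excludes subjects without a lead or data; the documents do not establish that.

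Next, 8.2 may settle the matter, and imputation could operate inside the restrictive reading on subjects with partial weeks 5-8 data. Both are possible. It would be wrong to say that an imputation rule or a sensitivity analysis is missing. But 6.2 must still agree with whatever 8.2 says, and 5.1 names early termination without limiting it to stops after week 4.

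Third, 6.2 openly declares a modified intent-to-treat approach, of which leaving out never-implanted subjects is a common form. Protocol 5.2 describes placement as the same in both arms apart from active stimulation, so there is little reason to expect no-lead losses to differ by arm. That is fair, and it weakens the no-lead half of the concern. It does less for losses during treatment: only one arm is stimulated, and Protocol 5.2.1 lets unblinded staff know the assignment.

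Two further inferences should not be drawn:

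- Protocol 4.4.1.1 says "Each randomized subject must obtain ≥ 50% reduction during weeks 5-8 of the treatment period", which might look like a third conflict. It defines success and not an analysis set, and even the first sentence of 6.2 is narrower than all randomized subjects.
- The coverage criterion in SAP 6.3, limited to Group #1, might look like a related fault. Coverage has no counterpart in a sham arm without stimulation, part of the criterion is blacked out, and the set is supportive.

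**Conclusion.** The point holds as an ambiguity in the primary analysis population that should be fixed; confidence is moderate. The first sentence of 6.2 with 5.1 supports one denominator. The second sentence, if applied as a condition, supports a smaller one.

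The size cannot be stated for this trial. On the assumed inputs, restriction moves the chance of a significant result for active, with no true difference, from about 1.3-1.5% to about 5-8% when outcome-related loss is 20% v 5%, and to about 0.4-0.5% when the loss is reversed. A reader might infer that restriction favours active stimulation; the documents give no loss rates that would support a direction. Equal loss, or loss unrelated to outcome, has little effect.

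Nor does restriction necessarily depart far from what 5.1 intends. It nearly equals own-arm imputation, and the gap opens under sham-rate or non-success rules. The 0.025 v 0.133 contrast is between restriction and counting non-successes, not between restriction and the plan's own, unseen imputation rule.

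**What to change.** - **SAP 6.2:** delete the lead and weeks 5-8 data qualifiers from the second sentence, so that every primary-TKR subject meeting the first sentence is analyzed in the randomized group.
- **SAP 5.1 and 8.2:** state in matching words that subjects with no weeks 5-8 data are handled by the imputation described there.
- **SAP 6.4:** align it. Adding attempted-but-no-lead subjects becomes redundant once the FAS plainly contains them.
- **Sensitivity analysis:** if 8.2 does not already have one, add an analysis counting subjects without weeks 5-8 data as non-successes.

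The cost is SAP wording and at most one extra analysis, with no new data. The primary p-value may change in either direction: in the one-trial example, from 0.025 under restriction to between 0.012 and 0.093 under the imputation rules shown, with 0.133 in the non-success analysis.
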